ANNEX 3: QUALITY OF LIFE QUESTIONNAIRES

1. FKSI-19 QUESTIONNAIRE

1	Pleas	w is a list of statements that other people wit te circle or mark one number per line to it					
t	the p	ast 7 days.					
1			Not at all	A little bit	Some- what	Quite a bit	Very much
	GP1	I have a lack of energy	0	1	2	3	4
	GP4	I have pain	0	1	2	3	4
	C2	I am losing weight	0	1	2	3	4
	HI7	I feel fatigued	0	1	2	3	4
	Bl	I have been short of breath	0	1	2	3	4
	BRJM3	I am bothered by fevers (episodes of high body temperature)	0	1	2	3	4
	BP1	I have bone pain	0	1	2	3	4
	L2	I have been coughing	0	1	2	3	4
	HI12	I feel weak all over	0	1	2	3	4
	RCC	I have had blood in my urine	0	1	2	3	4
	C6	I have a good appetite	0	1	2	3	4
	GF5	I am sleeping well	0	1	2	3	4
	GE6	I worry that my condition will get worse	0	1	2	3	4
	G#2	I have nausea	0	1	2	3	4
	CS	I have diarrhea (diarrhoea)	0	1	2	3	4
	GDS	I am bothered by side effects of treatment	0	1	2	3	4
	GF1	I am able to work (include work at home)	0	1	2	3	4
.	GF3	I am able to enjoy life	0	1	2	3	4
	GF7	I am content with the quality of my life right now	0	1	2	3	4
		sesse-Ralated Symptoms Subscale – Physical					

Please inform your doctor of any adverse event you have experienced

Subject ID:

2. RE AND MH DOMAINS OF SF-16 QUESTIONNAIRE

SF36 Health Survey

INSTRUCTIONS: This set of questions asks for your views about your health. This information will help keep track of how you feel and how well you are able to do your usual activities. Answer every question by marking the answer as indicated. If you are unsure about how to answer a question please give the best answer you can.

Items of Role-Emotional (RE) domains

5.	During the past 4 weeks , have you had any of the following problems with your work or other regular daily activities as a result of any emotional problems (e.g. feeling depressed or anxious)?										
	(Please circle one number on each line.)	Yes	No								
5(a)	Cut down on the amount of time you spent on work or other activities	1	2								
5(b)	Accomplished less than you would like	1	2								
5(c)	Didn't do work or other activities as carefully as usual	1	2								

Items of Mental-Health (MH) domains

9.	These questions are about how you feel and how things have been with you during the past 4 weeks. Please give the one answer that is closest to the way you have been feeling for each item.										
	(Please circle one number on each line.)	All of the Time	Most of the Time	A Good Bit of the Time	Some of the Time	A Little of the Time	None of the Time				
9(b)	Have you been a very nervous person?	1	2	3	4	5	6				
9(c)	Have you felt so down in the dumps that nothing could cheer you up?	1	2	3	4	5	6				
9(d)	Have you felt calm and peaceful?	1	2	3	4	5	6				
9(f)	Have you felt downhearted and blue?	1	2	3	4	5	6				
9(h)	Have you been a happy person?	1	2	3	4	5	6				

Please inform your doctor of any adverse event you have experienced

CC

Patient information Letter and Consent

Subject ID:

1 AMENDMENTS FROM PREVIOUS VERSION(S)

Not applicable.

2 INTRODUCTION

Note: in this document any text taken directly from the Non-Interventional (NI) study protocol is *italicised*.

2.1 STUDY DESIGN

This study is a European, prospective (partly retrospective), non-interventional, non-controlled, observational multicenter study. It will be carried out with specialists in charge of patients with adv/mRCC, from several EU countries including Austria, Belgium/Luxembourg, France, Greece, Italy, Spain, Switzerland, The Netherlands and UK (non-exhaustive list, additional countries may be considered at a later stage).

Study population:

Patients will be enrolled when they start a treatment with SU in 1st line or AXI in 2nd line post SU treatment (setting population). The possible sequences of treatment under investigation will be:

- SU (prospective) AXI
- SU (retrospective) AXI
- *SU* (prospective) no further active treatment (supportive care)
- *SU* (prospective) other 2nd line treatment options (sorafenib, pazopanib, everolimus, temsirolimus, cabozantinib, nivolumab, other)

The study is designed to enrol approximately 750 patients. Out of these, 350 are expected to receive the combined SU-AXI sequence (study population: "SU-AXI patients") and to meet primary outcome objectives.

[figure not shown]

Figure 1: Study Scheme

Inclusion and non-inclusion criteria:

Patients must meet all of the following inclusion criteria to be eligible for the study:

- Histologically confirmed diagnosis of advanced/metastatic renal carcinoma (clear cell RCC as well as non-clear cell RCC) with measurable disease according to RECIST1.1;
- Patients 18 years of age and over;
- Patients being treated with SU in 1st line according to the European therapeutic indication and/or being treated with AXI in 2nd line according to the European approved therapeutic indication (except post cytokines);
- Evidence of a personally signed and dated informed consent document indicating that the patient (or a legally acceptable representative) has been informed of all pertinent aspects of the study.

Patients meeting any of the following non-inclusion criteria will not be included in the study:

- Patients being treated with cytokines or any other treatment outside of SU in 1st line;
- Patients receiving anti-tumor treatment beyond a 2^{nd} line;
- Patients already under SU, already under AXI: enrollment must occur at the beginning of each line of treatment (before or at the first follow up visit).

Data sources:

Data will come from medical records and will be collected in routine clinical practice. Because of the inclusion criteria (Patients being treated with SU in 1st line according to the European therapeutic indication and/or being treated with AX! in 2nd line according to the European approved therapeutic indication (except post cytokines)) the medication is prescribed within the regular practice of the physician. As a non-interventional study, there are no specific requirements with regards to the treatment process.

The study will include:

- a retrospective data collection period consisting of SU 1st line treatment records for patients who start the study with AXI in 2nd line;
- *A prospective data collection period for all patients enrolled in the study (sociodemographic, treatment and medical data).*

The medical data collection methods used will be:

- *eCRF* (*electronic Case Report Form*) for physicians;
- Paper questionnaires for patients (assessment of the quality of life).

The Quality Of Life questionnaire will be completed at baseline and then every month for patients receiving AXI. QoL will also be measured at the discontinuation of AXI treatment. The physician will remit the QoL questionnaire to the patient and ask him/ her to complete it every month at home (i.e. Day 0 Day 30 Day 60 etc.). Patients will return it using pre-stamped envelopes. If not done before, the questionnaire will be completed at the site preferentially prior to the follow-up visit(s).

[figure not shown]
Observation period:

Patients will be enrolled for 3 years and followed-up for a minimum 2-year period, until the end of the study, whatever the therapeutic strategy post SU or post AXI. Visits will be naturalistic but follow-up visits are approximately expected:

- *during SU treatment: every 6 weeks (every cycle) with tumor assessment approximately every 3 months with respect to the clinical practice;*
- *during AXI treatment: every 4 weeks (every cycle) with tumor approximately assessment every 2 months with respect to the clinical practice;*

When patients come off SU treatment (i.e. are not receiving AXI) or come off AXI (after receiving the SU-INL sequence) they will be followed up every 6 months (separate form) for survival until the end of the study.

2.2 STUDY OBJECTIVES

Primary objectives:

In real life setting,

- To assess the impact of AXI in 2nd line post-SU on progression free survival (PFS) and on time to treatment failure (TTF) for patients with adv/mRCC;
- To assess the impact of the SU–AXI sequence on combined PFS and TTF for patients with adv/mRCC

Secondary objectives:

In real life setting,

- To assess the Objective Response Rate (ORR) for adv/mRCC patients receiving AXI in 2nd line post SU;
- To describe usage of flexible dosing of AXI in these patients in terms of dosing change, dosing schedules and the average dose received during the AXI period treatment;
- 3To assess the proportion of titrated patients within adv/mRCC patients receiving AXI in 2nd line post SU;
- 4To assess the impact of titration on PFS for adv/mRCC patients receiving AXI in 2nd line post SU;
- To assess the Overall Survival (OS) (OS median and 24-month OS) for adv/mRCC patients receiving SU in first line followed by AXI in 2nd line;
- To assess the time to strategy failure (TSF) for adv/mRCC patients receiving the SU–AXI sequence;
- To assess PFS and OS for the combined 1st line SU 2nd line sequences according to the second line post SU (TKI, mTOR) treatment;
- To describe safety and tolerability of patients receiving the SU-AXI sequence;
- To measure quality of life (QoL) in patients receiving AXI in 2nd line post SU.

3 INTERIM ANALYSES

A final report will present the results of analyses concerning follow-up of the patient cohort and will address the study objectives.

Specific annual descriptive analyses will be realized before the final analyses.

4 HYPOTHESES AND DECISION RULES

4.1 STATISTICAL HYPOTHESES

Not applicable.

4.2 STATISTICAL DECISION RULES

No statistical test will be performed. Whenever relevant, a two-sided 95% confidence interval will be provided.

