8.1.1 Descriptive Methods

Descriptive analysis of qualitative and ordinal variables will comprise the number and percentage of each category. Percentages will be calculated on the number of all available data, excluding missing data.

Descriptive analysis of quantitative variables will present the mean, the standard deviation (SD) as well as the median, quartile 1, quartile 3, min and max values.

The 95% confidence intervals will be presented for main endpoints. The 'exact' Clopper-Pearson confidence interval will be provided to assess 2-sided 95% confidence interval for main binomial proportions (e.g. ORR rate).

The number of missing values will be reported in the results table for each variable.

8.1.2 Survival Analysis Methods

The survival functions (for PFS, TTF, TSF, OS) will be estimated with the Kaplan-Meier method. The survival function S(t) is the probability that the event (treatment discontinuation, death or progression) does not occur before a specified time.

This method will be applied to derive, survival curves, median event time and a 95% confidence interval for the median survival time (time at which half the analyzed patients have presented the event). Survival curves will give an idea of whether or not the groups are proportional (i.e. the survival functions are approximately parallel). For OS, the share of patients alive at 24 months will also be measured.

The log-rank test of equality across strata will be used to compare survival curves for categorical variables (sub-groups of interest). For continuous variables, a univariate Cox proportional hazard regression will be used.

For analyses of prognostic factors of survival time, multivariate Cox proportional hazard regressions will be performed.

8.1.3 Strategy of Variable Selection in a Cox Model for PFS Analysis

The strategy of selection of variables in multivariate models will consist in: *Step 1: Selection of initial factor*

In a first step, the association between the PFS and each potential factor will be analyzed using

- A Log-Rank test (PROC LIFETEST under SAS 9.4) for categorical factors. Kaplan-Meier curves will also be presented in order to give an idea of whether or not the corresponding groups are proportional (i.e. the survival functions are approximately parallel)
- a univariate Cox proportional hazard regression (PROC PHREG under SAS 9.4) for continuous factors

Only significant factors at the 25% threshold will be retained for the initial model.

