The possible correlations between the factors selected will be investigated. This will be done using

- A Chi-2 or Fisher-exact tests (if at least one number is less than 5) for 2 categorical factors
- An Analysis of Covariance (ANCOVA) for 2 continuous factors or for a categorical and a continuous factor.

Since two highly correlated factors (p-value <5%) cannot be present in the same model, a clinical arbitration can be requested if necessary.

Step 2: Selection of final factors

For this step, a Cox model will be run (PROC PHREG under SAS 9.4). In a first step, all the factors retained at the end of step 1 will be introduced to the model. PFIZER CONFIDENTIAL

Then a backward elimination procedure will be used in order to retain only independently significant factors at the 5% threshold.

Step 3: Investigate possible interactions between final factors

When the final model has been reached, interactions will be introduced to verify their non-significance. The existence of an interaction between two variables means that the effect of one variable is different depending on the other variable; it will have to be taken into account in the interpretation.

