8.2.4 Analyses of Quality of Life Endpoints

Quality of life analyses will be provided in the FAS population on the SU-AXI subgroup. According to the questionnaire date, time windows will be derived according to the rule explain in section **Error! Reference source not found.** In case of missing or partial date, questionnaires will not be analyzed.

Quality of life will be analyzed using descriptive statistics at the treatment initiation, on the first 6 months and on AXI discontinuation overall and according to the best response observed under Axitinib treatment (CR, PR, SD, and PD):

- the FKSI-19 global score,
- the FKSI DRS-P subscore,
- the FKSI DRS-E subscore,
- the FKSI TSE subscore,
- the FKSI FWB subscore,
- the SF36 MH subscore,
- and the SF36 RE subscore.

Same analysis will be repeated on changes in scores/subscores from Baseline.

In order to explore possible variations in time and the possible differences according to the best response observed under Axitinib treatment, each changes in scores/subscores mentioned above will be analyzed using a mixed model for repeated measures (MMRM) according to the method described in section 8.1 of this document (Analysis of longitudinal data).

Estimated mean changes in scores/subscores from baseline will be provided and represented graphically with their 95% confidence interval:

- monthly (on the first 6 months),
- for each best response observed under Axitinib treatment (CR, PR, SD, and PD),
- in case of a statistically significant interaction between time and best response observed under Axitinib treatment, monthly estimated means will also be provided according to best response observed under Axitinib treatment (CR, PR, SD, and PD)

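### SAP 4.2 rules out all statistical tests, but SAP 8.1 to 8.2.4 plan several and make one quality-of-life output conditional on a significant interaction with no stated level

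*SAP*

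**What the plan says.** SAP 4.1 marks hypotheses as not applicable. SAP 4.2 then says "No statistical test will be performed" and adds "Whenever relevant, a two-sided 95% confidence interval will be provided". Neither sentence is limited to confirmatory tests or to the primary endpoints.

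Section 8 of the SAP prescribes the following:

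- **8.1.2 (survival methods):** "The log-rank test of equality across strata will be used to compare survival curves" for categorical sub-groups. No level is given.
- **8.1.3, step 1:** log-rank or univariate Cox tests of each candidate factor, with the rule "Only significant factors at the 25% threshold will be retained for the initial model". Correlation between the retained factors is then tested, for example by "A Chi-2 or Fisher-exact tests (if at least one number is less than 5) for 2 categorical factors", and p below 5% counts as highly correlated.
- **8.1.3, steps 2 and 3:** backward elimination to "retain only independently significant factors at the 5% threshold", followed by a check that interactions are non-significant.
- **8.2.2:** runs that strategy on PFS under axitinib, a primary endpoint.
- **8.2.4:** gives monthly model-estimated mean changes split by best response only "in case of a statistically significant interaction between time and best response observed under Axitinib treatment". No level is given.

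Protocol 8.5 calls the objective only descriptive. It also sizes a comparison of axitinib PFS with the AXIS trial: a Brookmeyer-Crowley type test, one-sided alpha 0.1, 80% power, 125 prospective SU-AXI patients. The SAP does not mention this test.

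**The concern.** The section that sets the decision rules says that there are none, and later sections contain several. Anyone working from the SAP must disregard either 4.2 or parts of section 8, and the document does not say which takes precedence.

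Two consequences follow. First, the p-values in section 8 have no stated status. Log-rank results between non-randomised sub-groups could be reported as tested differences in a study that describes itself as descriptive. Second, the condition in 8.2.4 is itself a decision rule, and its level is left open until the data are in hand. Whether a given score's monthly profile by response is shown would then depend on a test result and on a threshold chosen late.

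**Working it through.** **1. The protocol's own figure.** The only powered test in the documents is the AXIS comparison in protocol 8.5. Inputs: n = 125, expected median 6.5 months, lower limit 4.9 months (75% of 6.5 is 4.875), one-sided alpha 0.1. I assume exponential PFS and no censoring before 4.9 months.

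- S(4.9) = 0.5^(4.9/6.5) = 0.593.
- Standard error under the null: sqrt(0.25/125) = 0.0447. Under the alternative: sqrt(0.593 × 0.407/125) = 0.0439.
- Power = Φ[(0.593 − 0.5 − 1.2816 × 0.0447)/0.0439] = 79.2%.
- With the alternative variance throughout, power is 79.8%. At 4.875 months the two forms give 80.2% and 80.9%.

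The stated 80% is reproduced. This is a worked design element, so its absence from SAP 4.1 and 4.2 needs an explicit statement.

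**2. Section 4.2 against section 8.**

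| SAP section | Test planned | Level | Compatible with 4.2 as worded? |
|---|---|---|---|
| 8.1.2 | log-rank between sub-groups | none given | No |
| 8.1.3 step 1 | log-rank or univariate Cox screening | 25% | No |
| 8.1.3 step 1 | chi-square, Fisher or ANCOVA for correlation | 5% | No |
| 8.1.3 step 2 | backward elimination | 5% | No |
| 8.1.3 step 3 | interaction checks | none given | No |
| 8.2.4 | time-by-best-response interaction | none given | No |

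Section 8.2 does not name the log-rank test. Section 8.2.2 reaches it through its reference to the selection strategy in 8.1.

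**3. What the 8.2.4 condition covers.** The section lists four kinds of by-response output for seven scores (FKSI-19 total, four FKSI subscores, SF-36 MH and RE):

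- descriptive scores at initiation, over the first 6 months and at discontinuation: unconditional;
- the same for changes from baseline: unconditional;
- MMRM mean change for each best-response category: unconditional;
- MMRM mean change by month and best response: conditional on the interaction.

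Protocol 8.7.2 asks only that quality of life also be assessed by response to axitinib. The first three outputs do that.

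**4. Behaviour of the condition.** With six monthly windows and four response categories, the interaction has up to (6 − 1) × (4 − 1) = 15 degrees of freedom per score. If there is no true interaction, the chance that at least one of seven conditions opens is 1 − (1 − α)^7 under independence:

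- α = 0.01: 6.8%
- α = 0.05: 30.2%
- α = 0.10: 52.2%

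All three levels are assumptions, since the SAP states none. The scores are correlated, so the figures are rough; under complete dependence the chance would fall to α itself. They measure chance release, not suppression.

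The chance that a true interaction goes unreported depends on its strength, which the documents do not allow one to set. In a large-sample chi-square approximation with 15 degrees of freedom and α = 0.05, assumed noncentralities of 5, 10, 20 and 30 give 78%, 54%, 17% and 3%. No single figure for suppression can be defended.

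**The case against.** The best defence is context. The sentence in 4.2 stands under hypotheses and decision rules, directly after hypotheses are declared not applicable, in a study with a descriptive aim. Its author probably meant that no confirmatory test is performed. The thresholds in 8.1.3 are selection steps for a Cox analysis that protocol 8.7.1 itself foresees, and no efficacy claim rests on them. All of section 8 can be run, and no primary estimate changes. This is fair as to intent and consequence, and it keeps the point modest. It does not rescue the wording, because 4.2 contains no such limitation.

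Three stronger readings are tempting and are not supported:

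- **Quality of life by response is withheld unless the interaction is significant.** It is not. Three of the four by-response outputs are unconditional, every score is reported by response, and the commitment in protocol 8.7.2 is met. The conditional means are described as additional.
- **The 30% figure shows how often results would be suppressed.** It is the chance of at least one release when nothing is there, at an assumed level. Nor do the documents support saying that modest true differences would usually be withheld (working, step 4).
- **The log-rank tests must be replaced by hazard ratios.** That is a preference. A single hazard ratio relies on proportionality, which 8.1.2 checks only by looking at the curves. Log-rank tests may stay if labelled exploratory.

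**Conclusion.** The point holds in a limited form. SAP 4.2 is incorrect as written, because 8.1.2, 8.1.3, 8.2.2 and 8.2.4 all plan or apply tests. This follows from the text and rests on no numerical assumption. Section 4 is also out of step with protocol 8.5, whose AXIS comparison the SAP neither keeps nor drops.

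The effect on quality of life is confined to one output per score: the monthly model means split by best response, for seven scores, reported selectively on a test of unstated level. The documents give no basis for quantifying how often that profile would be lost. The primary Kaplan-Meier results for PFS and TTF are unaffected. The correction is worth making because the present statement is false and the remedy is nearly free.

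**What to change.** 1. **SAP 4.2:** replace the sentence with one saying that no confirmatory test is performed, and that p-values arising in section 8 are nominal, two-sided, exploratory and not adjusted for multiplicity. Log-rank tests can remain under that label.
2. **SAP 4.1 and 4.2:** state whether the one-sided 0.1 Brookmeyer-Crowley type comparison with AXIS from protocol 8.5 is kept or dropped. If it is kept, the new wording of 4.2 must name it as the exception.
3. **SAP 8.2.4:** delete the significance condition and always give the monthly estimated means by best response, with 95% confidence intervals and the number of patients in each cell. The model in 8.1.4 already contains the interaction, so no new analysis is needed.

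The cost is a change of SAP wording and a few more tables. Some cells will be sparse, complete responders being the likely case, which is why the numbers should be printed beside the estimates.

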5 ANALYSIS SETS/POPULATIONS

5.1 FULL ANALYSIS SET

The Full Analysis Set (FAS) refers to all eligible patients enrolled in the study, whatever the therapeutic strategy used during the observation period: i.e. patients enrolled when they start a treatment with SU in 1st line or AXI in 2nd line post SU treatment.

